11.1 Approval of committees

This study will be conducted in accordance with the standards of the Declaration of Helsinki, World Medical Association 2013. Nuremberg Code; Nuremberg Judgment by the International Tribunal at Nuremberg, 1947. Belmont Report, National Commission for the Protection of Subjects of Biomedical and Conduct Research, 1979. It will be conducted in accordance with the scientific and technical requirements necessary for the registration of medicines for human use of the International Conference on Harmonization (The International Council for Harmonisation (ICH) Guideline for Good Clinical Practice. International Ethical Guidelines for Biomedical Research Involving Human Subjects of the Council for International Organizations of Medical Sciences of Medical Sciences, CIOMS, 2002). International Ethical Guidelines for Epidemiological Studies of the Council for International Organizations of Medical Sciences of Medical Sciences, CIOMS, 2008). The Research Ethics Committee and the Research Committee will evaluate the protocol before conducting the study and will issue their approval or any possible modifications for its implementation. These Committees must be notified of any significant changes to the protocol. In addition to the above, the current regulations of the regulatory authority must also be complied with.

The sponsor's authorized personnel will submit the essential documentation of the research project for evaluation by the Research Ethics Committees, Research Committees, and when applicable, to the Biosafety Committee: research protocol, informed consent form, researcher's manual, subject material, as well as other additionally requested documents, in accordance with the local, national or international requirements applicable by regulatory entities.

The study will not be initiated at the research center without the confidentiality agreements and financial proposals from each of the principal investigators, duly signed, and without having previously obtained the favorable opinion and/or approval of the corresponding Research Ethics Committees, Research Committees, and, where applicable, the Biosafety Committee.

The study will not begin without meeting the relevant local, national, or international regulatory requirements and obtaining the appropriate health authorization.

The study is considered to be research with greater than minimum risk, in accordance with the Regulations of the General Health Law on Health Research, Title Two, Chapter I, Article 17, Section III, published in the Official Gazette on January 6, 1987.

11.2 Amendments to the protocol

The amendment process will be relevant when there is a need to make any changes to a document that is part of the research project or protocol, due to changes in the methodological structure, replacement of the principal investigator, or the identification of risks to the research subjects. Documents that may be amended include: the protocol, informed consent letter, researcher's manual, subject documents, measurement scales, and activity schedule.

Any amendment must be approved by the sponsor and/or the principal investigator. The amended document(s), once reviewed and approved by the Research Ethics Committee and the Research Committee or, when applicable, by the Biosafety Committee (entities that issued the initial favorable opinion for the conduct of the research), will be sent for authorization by COFEPRIS.

Amendments that substantially modify the protocol or impose additional or different risks to research subjects must be approved by the aforementioned Committees. It is the investigator's responsibility to

take measures in situations requiring immediate action to prevent unnecessary harm to study participants.

The principal investigator is responsible for communicating to the Research Ethics Committee any amendments to the protocol that could affect the rights, safety, or well-being of the research participants. They must also report any situation or new knowledge that indicates an increased risk to the participants, the premature termination or suspension of the study, the reasons for this, and the results obtained to that point. They must also report the conclusion of the study upon completion of the research protocol.

11.3 Early termination of the study

The study may be temporarily suspended or terminated prematurely if there is sufficiently reasonable cause. Written notification documenting the reason for the suspension or early termination must be provided by the party executing the suspension. The PI must promptly inform the study participants, the IC, and the IRB, providing the reasons.

Situations in which suspension or early termination of the study will be considered include, but are not limited to:

1. The presence of serious adverse events in more than 10% of participants in a study group.
2. The regulatory authority (COFEPRIS) considered it due to security alerts.
3. The Sponsor determines this for its convenience or eventualities such as: financial support, manufacturing errors, etc.
4. The determination of unexpected risks to participants that are significant or unacceptable.
5. Obtaining new relevant safety information.
6. Insufficient adherence to protocol requirements.
7. The data obtained are not evaluable or are not sufficiently complete.
8. The determination that the primary objective has been achieved.
9. The determination of futility.

In the event of suspension, the study may be resumed once the situations that led to the suspension have been resolved, provided this justification is sufficient for the sponsor, IC, IEC, and regulatory authorities.

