10.1.2 Data interpretation

The results of continuous quantitative variables will be presented in measures of central tendency: mean, standard deviation and ranges.

KS and SW tests will be performed, as applicable, to determine whether the distribution presents normality in the results obtained in each study group. [44]

If normality of the data is observed ($p > 0.05$; for KS and SW), the statistical analysis of the continuous quantitative variables to find significant differences (p) will be as follows:

- Intra-group analysis: will be determined using the Student's t-test for repeated measures.
- Between-group analysis: differences between groups will be analyzed using Student's t-test for independent groups.

For $p < 0.05$ in KS and SW, the statistical analysis of continuous quantitative variables to find significant differences (p) will be as follows:

- Intra-group analysis: will be determined using the Wilcoxon rank test. [45]
- Between-group analysis: differences between groups will be analyzed using the Mann-Whitney U statistic.

The level of difference to consider significance will be an α of 0.05 or less [46].

The results of the nominal and ordinal qualitative variables will be presented in frequencies, proportions and percentages.

Statistical analysis to identify significant differences in qualitative variables will be performed by creating 2x2 contingency tables and will be carried out as follows:

- Intra-group differences: will be determined by the McNemar test [47], which is applied to 2x2 contingency tables with a dichotomous trait and pairs of matched subjects to determine whether the marginal frequencies of row and column are equal (marginal homogeneity).
- Difference between groups: Differences between groups will be analyzed using Pearson's X^2 test or Fisher's exact test when expected values are less than 5.

The level of difference to consider significance will be an α of 0.05 or less.

For the reporting of adverse events, participants who were randomly assigned to an intervention group after application of the investigational product will be considered.

The final results report will be displayed in tables or graphs, as appropriate.

The investigational product will be considered safe when there are no clinical and statistical differences in all primary outcome variables, with respect to its comparator (Healon EndoCoat®).

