10.2.2 Justification of the sample calculation

Although there are no references on sample size calculation for pilot studies, it was considered appropriate to perform the calculation based on the clinical study by Storr-Paulsen et al [48], who compared the influence of three OVDs of 1%, 2% and 3% SH on corneal endothelial cell count during cataract surgery up to three months postoperatively. All three OVDs showed a decrease in postoperative cell count, for SH-1% it was 18.46%, for SH-2% it was 18.03% and for SH-3% it was 6.97%. [48]

The percentage decrease in dispersive OVD at 3% SH was considered. The sample size was calculated using the equation for an equivalence ratio [49], which is useful when we want to test whether a ratio p , is different from a standard reference value, p_0 . In this case, we want to test that PRO-149 is equivalent to its comparator (Healon® EndoCoat). Here the test falls on PRO-149; that is, equivalence is represented by the alternative hypothesis (H_1), rather than the null hypothesis (H_0).

Working hypothesis for calculating the sample size:

$$H_0: |P - P_0| \geq \delta$$
$$H_1: |P - P_0| < \delta$$

Considering an $\alpha = 0.05$ corresponding to the type I error (95% confidence level), a power (β) = 0.20 corresponding to the type II error (80% power) and a test margin (δ) of 5%. The calculation to estimate the sample size was performed using an online tool (*Sample size calculators*, <http://powerandsamplesize.com>), following the following equations:

$$n = p(1-p) \left(\frac{Z_{1-\alpha} + Z_{1-\beta/2}}{|p - p_0| - \delta} \right)^2$$

$$1 - \beta = 2[\Phi(z - z_{1-\alpha}) + \Phi(-z - z_{1-\alpha})] - 1, z = \frac{|p - p_0| - \delta}{\sqrt{\frac{p(1-p)}{n}}}$$

Where:

n: sample size,

p₀: comparison value,

Φ: function of the standard normal distribution

Φ⁻¹: normal standard quantile function

α: Type I error

β: Type II error (1-β is the power)

δ: test margin.

According to the previous calculation, the result was 14 cases (eyes) per arm; this calculation was increased by 20% to account for potential losses. The total sample size required is 18 cases (eyes) per treatment arm, a total of 36 cases. This calculation is consistent with the sample size used in similar clinical studies where OVDs were employed. [50, 51, 52]

11. Ethical considerations

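### Section 11.3 lets the study end because its primary objective is judged achieved, with no interim plan and a success rule whose statistical half is easier to meet with fewer subjects

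*Combined protocol and SAP*

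**What the plan says.** Section 11.3 gives an open-ended list of situations in which suspension or early termination will be considered. Item 8 is "The determination that the primary objective has been achieved" and item 9 is "The determination of futility". Neither carries a criterion, a time point or a body that decides.

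Section 10 describes a single analysis by sponsor staff, with no interim look, stopping boundary or allowance for repeated testing. For normally distributed outcomes, "differences between groups will be analyzed using Student's t-test for independent groups"; Mann-Whitney is used otherwise. On the level, "The level of difference to consider significance will be an α of 0.05 or less".

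The success rule in section 10.1.2 is: "The investigational product will be considered safe when there are no clinical and statistical differences in all primary outcome variables", relative to the comparator. The primary outcomes are change in corneal endothelial cell (CEC) density and intraocular pressure (IOP). No clinically relevant difference is defined for the analysis. A 5% margin appears only in section 10.2.2, where the sizing argument says that "equivalence is represented by the alternative hypothesis".

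**The concern.** In a superiority trial, stopping early for success requires strong evidence. Here the statistical part of success is a non-significant test, which weak evidence supplies. An early determination under item 8 can therefore be made most easily when the data are least able to reveal a difference. The sponsor analyses the data and owns the database, and the trial is open-label. Coding the groups for the analysts does not remove the opportunity, because a test for no difference needs only two coded groups.

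At stake is the chance that a product truly worse than its comparator is reported as safe after a small, unplanned look. Nothing in the plan limits how often that chance may be taken.

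**Working it through.** The plan gives no figure for early stopping, so there is none to reproduce. The check asks how often the plan's between-group test is non-significant when a true difference exists.

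**Inputs**
- Test: two-sample t-test at 0.05 (section 10.1.2). Sidedness is not stated; two-sided is assumed.
- Sample sizes: 18 per arm (section 10.2.1) and 14 evaluable per arm (section 10.1.4). The sizes 6 and 12 are illustrative.
- SD of percentage CEC change: none is stated for this trial. Section 2.2.1 reports, for the comparator's 400-patient study, a 90% confidence interval of 0.23 to 4.33 with 200 per arm. The SE is (4.33 − 0.23) / (2 × 1.645) = 1.246, so the SD is 1.246 / √(2/200) = 12.46 points. That endpoint is at 3 months; this trial measures at day 29. The value is an assumption.

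**Feasibility of an early look.** At one subject per 4 days and about 45 days each (section 4.3), 12 subjects have finished by about day 12 × 4 + 45 = 93, inside the 4-month recruitment period. That is 6 per arm if balanced.

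**Single look.** With true standardised difference d, df = 2n − 2 and noncentrality λ = d√(n/2), the chance of non-significance is F(t₀.₉₇₅; df, λ) − F(−t₀.₉₇₅; df, λ), where F is the noncentral t distribution. A 10-point CEC difference is d = 10 / 12.46 = 0.80.

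| n per arm | critical t | λ, d = 1 | non-significant, d = 1 | λ, 10 points | non-significant, 10 points |
|---|---|---|---|---|---|
| 6 | 2.228 | 1.732 | 65% | 1.390 | 76% |
| 12 | 2.074 | 2.449 | 35% | 1.966 | 53% |
| 14 | 2.056 | 2.646 | 28% | 2.123 | 47% |
| 18 | 2.032 | 3.000 | 17% | 2.408 | 35% |

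**Three looks.** Simulation of 200,000 trials with cumulative data at 6, 12 and 18 per arm, counting a pass if any look is non-significant:
- d = 1: 69%, against 17% at the final look only.
- 10 points, SD 12.46: 81%, against 35%.

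**Sensitivity to the SD, true difference 10 points.** At SD 8, non-significance is 50% at 6 per arm and 5% at 18, and three looks give 52%. At SD 15 it is 82% at 6 and 51% at 18. The levels move a good deal; the direction does not.

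**The case against.** Several points on the other side stand in part.

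- **The rule has a clinical half and covers all primary outcomes.** If the observed CEC difference also had to lie within 5 points (an assumption, since no limit is defined), the pass rate at d = 1 with SD 12.46 would be 14% at 6 per arm and 18% over three looks. With a true difference of exactly 5 points it would be 42% at 6 and 49% at 18, so a small sample would then give no advantage at a single look. One independent IOP test with no true difference lowers 65% to 0.65 × 0.95 = 62%; three such tests lower it to 0.65 × 0.95³ = 56%.
- **Section 10.1.4 says the objective needs 28 evaluable subjects, 14 per arm.** This argues against declaring success at 6 per arm. At 14 the effect is far smaller (28% against 17%). The text does not, however, tie item 8 to that number.
- **There are procedural safeguards.** Termination is only considered, needs a reasonable cause with written reasons, and is reported to the committees. The committees are informed; they are not asked to judge whether the objective was met. A separate Monitoring Plan exists but is described only for monitoring activities.
- **No harm is shown for item 9.** A futility stop does not yield a conclusion of safety.

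A reader might infer that a small early sample meets the objective almost by default. The documents do not support that, given the clinical half, the IOP requirement and section 10.1.4. A reader might also infer that repeated looks would double false equivalence, from 5% to about 10%, under two one-sided tests. That needs a margin of about 1 SD or more. At the 5-point margin and SD 12.5, false equivalence is about 0.02% at the final look and 0.03% with three looks.

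**Conclusion.** The concern holds in limited form. Item 8 is a written ground for stopping with no plan behind it, and the statistical half of the success rule becomes easier to satisfy as the sample shrinks. For one outcome, an early look at 6 per arm passes that half 65% of the time at a true 1-SD difference, against 17% at the planned 18. Three looks take the 10-point CEC case from 35% to 81%.

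The result rests on a two-sided t-test, an illustrative look schedule and, for the CEC scale, an SD borrowed from a 3-month endpoint. It does not show that the sponsor intends such looks, nor that the full rule would pass at these rates. Using absence of difference as proof of equivalence is a separate weakness. Repairing it would not supply the missing interim plan.

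**What to change.** Delete item 8 from section 11.3, and item 9 for consistency because no futility rule exists. Add to section 11.3, with a cross-reference in section 10.1.2:

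> No interim between-arm comparison of the primary outcomes will be made to judge whether the objective has been met; the success rule in 10.1.2 will be applied once, after the last subject's final visit. If the study ends early for any other reason, including those in item 3, results will be descriptive and no conclusion of safety equivalence will be drawn. Review of CEC, IOP and adverse event data for subject safety is not restricted.

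The second sentence is needed because item 3 and the open-ended list would still permit other stops. The third keeps the safety grounds for stopping workable, since CEC and IOP are themselves safety outcomes. If the sponsor wants an early-success option, it should instead state the looks, the criterion and who decides.

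The cost is a wording amendment. The sponsor gives up an early-success option for which it has no plan.

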11.4 Informed consent

The ICF contains complete and understandable information about the study and the investigational product, in accordance with current applicable regulations and Good Clinical Practices.

The ICF will be considered a source document and will be filed as such. The site's principal investigator is responsible for ensuring that all new versions of the informed consent form undergo the appropriate approvals (the same ones that the original informed consent form underwent) and that the most current approved version is presented to the study subjects.

11.4.1 Obtaining

Informed consent must be obtained before the subject undergoes any procedure indicated in the protocol. For this purpose, the informed consent form must be signed.

Written consent documents will incorporate the elements of informed consent described in the Declaration of Helsinki and the ICH Guidelines for Good Clinical Practice and will be in compliance with all applicable laws and regulations.

The PI, or the study staff delegated by him or her, will provide the potential participant with all information regarding the characteristics of the study, its potential benefits, risks, objectives, and procedures.

This information will be provided in a language understandable to the subject. The subject will be explained that they have the right to discontinue their participation in the study at any stage, without affecting their relationship with the researcher and/or their future participation. Informed consent will be presented to the potential participant; they must have sufficient time to review each and every aspect mentioned above. Any questions they may have will be clarified by the person responsible for obtaining informed consent.

Once the participant agrees to participate in the study, he or she must sign and date the informed consent letter in the presence of two witnesses, whether or not related to the study subject. These witnesses will participate in the informed consent process and sign, confirming that the process was carried out prior to any study procedure, that the study information was clearly explained, and that any questions were clarified.

In the event that a subject is illiterate, acceptance will be specified with his or her fingerprint, and in the event that the subject is not capable of providing adequate written informed consent, a "legally authorized" representative of the subject may provide such consent for the subject in accordance with applicable laws and regulations.

Likewise, the PI, or the study staff delegated by him, must sign and date this consent.

The ICF must be signed in duplicate by all involved; one copy will be filed in the researcher's folder and the other will be given to the participant. The PI or designated staff member must document the process of obtaining Informed Consent through a detailed, accurate, and contemporaneous medical note, specifying the signed version, the date the document was signed, and how the process was carried out.

11.4.2 Special considerations

The procedures that will be performed during the conduct of the study do not pose any additional risk that should be considered apart from the procedures listed in the informed consent.

11.4.3 Modifications to informed consent

Any change to the ICF constitutes an amendment to this document and must be submitted for approval to the Research Ethics Committees and COFEPRIS.

Such amendments may be implemented only after obtaining written approval from the Research Ethics Committee and the Regulatory Body (as applicable), except for an amendment that is required to eliminate an immediate danger to the study subjects.

A re-consent process must be conducted for each subject affected by the amendment under the same conditions as those described above, in order to promptly communicate the new information contained in the document. The subject will be given an original signed amendment, and the researcher will retain the second original amendment.

11.5 Confidentiality

All documents and information provided to the research center by the sponsor are strictly confidential. The PI expressly agrees that the data regarding his or her professional and clinical experience, provided to the sponsor in paper form and stored electronically, are solely for use in connection with his or her activities with the clinical study sponsor, in accordance with Good Clinical Practice.

The PI agrees that he and his team members will use the information only within the scope of this study, to carry out the protocol. This agreement is binding as long as the confidential information has not been publicly disclosed by the sponsor.

The clinical study protocol provided to the PI may be used by the PI and his or her team to obtain informed consent from the subjects for the study. The clinical study protocol, as well as any information derived from it, must not be disclosed to other parties without the sponsor's written authorization.

The PI will not disclose any information without the prior written consent of Laboratorios Sophia, S.A. de C.V., except to representatives of the Competent Authorities, and only at their request. In the latter case, the researcher is obligated to inform Laboratorios Sophia, S.A. de C.V. before disclosing the information to these authorities.

The PI will complete and maintain a subject selection log, as well as the identification and enrollment list of each subject participating in the study. The researcher agrees to grant on-site access to the auditor and/or representatives of the Competent Authorities. The information will be treated in compliance with professional secrecy.

In the eCRF and all communications related to study subjects, they will be identified only by their study subject identification number, either the screening number or the randomization number. The information collected in this study will be exchanged between the sponsor and the research site and must be treated confidentially. The Health Authority, the IRB, the IC, the sponsor, the monitors/auditors, and third-party auditors will be the only bodies authorized to review the study documentation. If publications arise from this research project, under no circumstances will they contain information about the identification of the study subjects. If the study results are published, no personal information about the study subjects will be disclosed.

The protection of personal data will be in accordance with the corresponding current regulations.

[11.6 Conflict of interest](#)

The independence of the study's conduct and results from any actual or perceived external influences is critical. Therefore, any current conflict of interest of any person playing a role in the design, conduct, analysis, publication, or any other aspect of this study will be declared. Furthermore, those with a perceived conflict of interest will be asked to manage it in a manner appropriate to their participation in the study.

[11.6.1 Declaration of interests](#)

The PI agrees to declare his or her financial interests and conflicts of interest prior to the start of the study.

[11.7 Access to information](#)

The final study database will be the property of Laboratorios Sophia, S.A. de C.V., and access to it will be restricted. The PI will not have access to it except with prior written authorization from the sponsor.

Any information obtained that is relevant to the safety of the subjects participating in the study must be immediately shared with the research center, so that the study subjects can be notified.

